# **12.3 IDEEL derivation**

IDEEL is a 57-item questionnaire developed by Abetz et al. [4], that that assess the impact of dry eye symptoms on everyday life. The possible range of each IDEEL score was 0 (complete disability) to 100 (no disability). This questionnaire consists of 3 modules:

- Dry eye Treatment satisfaction & Bother (10 questions) comprising two sections: "Treatment In General" and "Treatment- Eye drops".
- Dry eye Quality of Life (27 questions) comprising three sections: "Daily activities", "Feelings" and "Work".
- Dry eye Symptom Bother (20 questions).

Rules for the calculation of the IDEEL dimension scores are reported in Table 4 and Table 5.

#### Table 4: Calculation of IDEEL dimension scores

| Parameter          | Calculation  |
|--------------------|--|
| Item scaling       | 
 
Dry Eye Treatment Satisfaction module: 
 
Items 1-5 are scored on a 5-point Likert-like scale from 0 "none of the time" to 4 "all of the time"
 
Items 6, 8-10 are scored on a dichotomous scale: 1 "Yes", 0 "No". This item is not included in the calculation of the scores.
 
 
 
Dry Eye Impact on Daily Life module: 
 
Items 1-9 are scored on a 5-point Likert-like scale from 1 "all of the time" to 5 "none of the time". Patients can also answer "I can no longer do this activity due to my dry eyes" (scored 0) or "I did not do this activity for reasons other than my dry eyes / Not applicable" (coded 6 but scored 5 for calculation of the scores)
 
Items 10-21, 23-27 are scored on a 5-point Likert-like scale from 0 "all of the time" to 4 "none of the time"
 
Item 22 is scored on a dichotomous scale: 1 "Yes", 0 "No". This item is not included in the calculation of the scores
 
 
 
Dry Eye Symptom-Bother module: 
 
Items 1 is scored on a 5-point Likert-like scale from 0 "all of the time" to 4 "all of the time"
 
Items 2-20 are scored on a 4-point Likert-like scale from 1 "not at all" to 4 "very much". Patients can also answer "I did not have this symptom / Not applicable" (scored 0).
 
 
 
  |
| Weighting of items | All items are given equal weight in the calculation of the scores.   |
| Range of scores    | 0-100 scales.  |
| Scoring procedure  | 
 
Dry Eye Treatment Satisfaction module: 
 
Satisfaction with Treatment Effectiveness score: If patients never use treatment for their dry eyes (answer is 0 "none of the time" to item 1) then items 2-5 are missing, and the Satisfaction with Treatment Effectiveness score is missing. The Satisfaction with Treatment Effectiveness score is calculated if at least 50% (2 items) of the 4 items within the dimension are completed, non-missing; otherwise the score is set to missing. The Satisfaction with Treatment Effectiveness score is calculated as the mean of the non-missing item scores 2-5 multiplied by 25.
 
Treatment-Related Bother score: If patients never use treatment for their dry eyes (answer is 0 "none of the time" to item 1) then item 6 is missing. The Treatment-Related Bother score is calculated if at least 50% (2 items) of the 4 items within the dimension; otherwise the score is set to missing. The Treatment-Related Bother score is calculated if at least 50% (2 items) of the 4 items within the dimension; otherwise the score is set to missing. The Treatment-Related Bother score is calculated if at least 50% (2 items) of the 4 items within the dimension are completed, non-missing; otherwise the score is set to missing. The Treatment-Related Bother score is calculated as the mean of the non-missing item scores 6, 8-10 multiplied by 25.
 
 
 
Dry Eye Impact on Daily Life module: 
 
Impact on Daily Activities score: Response "I did not do this activity for reasons other than my dry eyes / Not applicable" for items 1-6 is re-coded 5 instead of 6. Other responses are scored with the original response code. The Impact on Daily Activities score is calculated as the mean of the non-missing. The Impact on Daily Activities score is calculated as the mean of the non-missing. The Impact on Daily Activities score is calculated as the mean of the non-missing. The Impact on Daily Activities score is calculated as the mean of the non-missing. The Impact on Daily Activities score is ca

 |

| Parameter  | Calculation   |
|--|---|
|  | 
 
Impact on Work score: If patients are not currently working (answer is 0 "No" to item 22) then items 23-27 are missing, and the Impact on Work score is missing. The Impact on work score is calculated only when patients answer "Yes" to "Are you currently working?". The Impact on Work score is calculated if at least 50% (3 items) of the 5 items within the dimension are completed, non-missing; otherwise the score is set to missing. The Impact on Work score is calculated as the mean of the non-missing item scores 23-27 multiplied by 25.
 
Dry Eye Symptom-Bother module:
 
The Symptom Bother score is calculated if at least 50% (10 items) of the 20 items within the dimension are completed, non-missing; otherwise the score is set to missing; otherwise the score is set to missing. The Symptom Bother score is calculated as the mean of the non-missing item scores 1-20 multiplied by 25.
 
 |
| Interpretation and
method of treating
missing data | All the scores are calculated only if at least 50% of the items of the dimension are completed; otherwise, the scores are missing.  |

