# 10.2.2 Analysis details

Analysis of key secondary endpoints are detailed below in sections 10.2.2.1 - 10.2.2.6 and p-values to be evaluated for comparison between treatments in a sequential order are the following:

- 1. P-value of treatment variable from logistic regression model on proportion of patients reaching a value of Schirmer I test (without anesthesia) >10mm/5min at week 8 (section 10.2.2.1),
- 2. P-value of treatment variable from ANCOVA regression model on change from baseline in SANDE score for severity at week 12 (section 10.2.2.2),
- 3. P-value of treatment variable from ANCOVA regression model on change from baseline in SANDE score for frequency at week 12 (section 10.2.2.3),
- 4.1 P-value of treatment variable from MMRM regression model on IDEEL Quality of Life module at week 12 (section 10.2.2.4),
- 4.2 P-value of treatment variable from MMRM regression model on IDEEL Dry eye Treatment satisfaction & Bother module at week 12 (section 10.2.2.4),

- 4.3 P-value of treatment variable from MMRM regression model on IDEEL Dry eye Symptom bother module at week 12 (section 10.2.2.4),
- 4.4 P-value of treatment variable from MMRM regression model on IDEEL Quality of Life module at week 4 (section 10.2.2.4),
- 4.5 P-value of treatment variable from MMRM regression model on IDEEL Dry eye Treatment satisfaction & Bother module at week 4 (section 10.2.2.4),
- 4.6 P-value of treatment variable from MMRM regression model on IDEEL Dry eye Symptom bother module at week 4 (section 10.2.2.4),
- 5.1 P-value of treatment variable from MMRM regression model on Change from baseline in Cornea and conjunctiva vital staining with fluorescein NEI scale at week 4 (section 10.2.2.5),
- 5.2 P-value of treatment variable from MMRM regression model on Change from baseline in Cornea and conjunctiva vital staining with fluorescein NEI scale at week 8 (section 10.2.2.5),
- 5.3 P-value of treatment variable from MMRM regression model on Change from baseline in Cornea and conjunctiva vital staining with fluorescein NEI scale at week 12 (section 10.2.2.5),
- 6.1 P-value of treatment variable from MMRM regression model on Change from baseline in TFBUT values at week 4 (section 10.2.2.6),
- 6.2 P-value of treatment variable from MMRM regression model on Change from baseline in TFBUT values at week 8 (section 10.2.2.6),
- 6.3 P-value of treatment variable from MMRM regression model on Change from baseline in TFBUT values at week 12 (section 10.2.2.6).

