#### Table 5: Summary of dimensions and clusters of items of the IDEEL questionnaire

| Module                            | Dimensions                                | Number of
items | Cluster of
items | Direction of dimension scores                                    |
|-----------------------------------|---|--------------------|---------------------|--|
|                                   | Impact on Daily Activities                | 6                  | 1-6                 | Higher score = less impact on daily activities                   |
| Dry Eye Impact on
Daily Life   | Emotional Impact due to Dry Eye           | 11                 | 10-20               | Higher score = less emotional impact                             |
|                                   | Impact on Work due to Dry Eye             | 5                  | 23-27               | Higher score = less work impact                                  |
| Dry Eye Symptom-
Bother        | Dry Eye Symptom-Bother                    | 20                 | 1-20                | Higher score = greater symptom bother                            |
| Dry Eye Treatment
Satisfaction | Satisfaction with Treatment Effectiveness | 4                  | 2-5                 | Higher score = greater satisfaction with treatment effectiveness |
|                                   | Treatment- Related Bother / Inconvenience | 4                  | 6, 8-10             | Higher score = less treatment related bother                     |

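### SAP Table 4 codes IDEEL items 6 and 8-10 as 0/1 and bars them from scoring, yet builds the Treatment-Related Bother score from those four items alone, so the stated 0-100 range cannot be reached as written

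*SAP*

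**What the plan says.** SAP 12.3 scores the IDEEL in three modules. The Treatment satisfaction & Bother module has two dimensions in Table 5: Satisfaction with Treatment Effectiveness (items 2-5) and Treatment-Related Bother (items 6 and 8-10).

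- **Item scaling, Table 4.** For the four bother items: "Items 6, 8-10 are scored on a dichotomous scale: 1 'Yes', 0 'No'. This item is not included in the calculation of the scores". No scale is given for item 7.
- **Scoring procedure, Table 4.** "The Treatment-Related Bother score is calculated as the mean of the non-missing item scores 6, 8-10 multiplied by 25". The score is "calculated if at least 50% (2 items) of the 4 items within the dimension are completed, non-missing".
- **Range and direction.** SAP 12.3 and Table 4 put every IDEEL score on 0-100. Table 5 gives the bother dimension as "Higher score = less treatment related bother".
- **Symptom-Bother item 1, Table 4.** "Items 1 is scored on a 5-point Likert-like scale from 0 'all of the time' to 4 'all of the time", so both ends carry the same label.
- **Use.** SAP 10.2.2 lists as test 4.2 the "P-value of treatment variable from MMRM regression model on IDEEL Dry eye Treatment satisfaction & Bother module at week 12"; test 4.5 is the same module at week 4. SAP 10.2.2.4 makes the IDEEL comparisons one-sided.

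**The concern.** The item-scaling row and the scoring row of Table 4 cannot both be obeyed. One removes items 6 and 8-10 from all scores; the other forms a score from nothing else. Even if the exclusion is ignored, a Yes/No item multiplied by 25 does not fill a 0-100 scale. Direction is also open: the item wording is not given, so nobody can tell from the SAP whether coding Yes as 1 makes a higher score mean less bother, as Table 5 requires.

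The key secondary endpoints are tested in a fixed order and each test depends on the one before. If test 4.2 fails because of how the module was scored, the tests after it, including all NEI staining and TFBUT tests, cannot be claimed. If the rule is settled only after unblinding, the choice could also look driven by results.

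**Working it through.** **Inputs.** From Table 4: item codes, mean of non-missing items, multiplier 25, and at least half the items completed. From Table 5: the items in each dimension. From SAP 10.2.2: the order of tests.

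**1. Reproduce the stated range where the table is coherent.** Score = mean of completed items x 25.
- Satisfaction, items 2-5 coded 0-4: minimum 0 x 25 = 0; maximum 4 x 25 = 100.
- Impact on Work, items 23-27 coded 0-4: likewise 0 to 100.

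Both match the stated 0-100, so the formula is being read correctly.

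**2. Bother score with the exclusion applied.** Usable items: 4 - 4 = 0. Required: 2. The score is missing for 100% of patients.

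**3. Bother score with the exclusion ignored and 0/1 coding kept.** Minimum 0 x 25 = 0; maximum 1 x 25 = 25. With all four items answered, the only possible values are 0, 6.25, 12.5, 18.75 and 25.

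**4. Codings that restore 0-100.**
- Items 0-4, multiplier 25: 4 x 25 = 100.
- Items 0/1, multiplier 100: 1 x 100 = 100.

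The documents do not say which is meant. Under either, the exclusion cannot apply to items 6 and 8-10.

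**5. What this does to a test.** For the same 0/1 answers, multipliers 25 and 100 differ by a constant factor of four. The MMRM uses change from baseline with baseline as covariate, and the imputation model is Gaussian. Estimate and standard error are therefore both divided by four, and the dimension's p-value stays the same. It does not stay the same if the score is missing, if graded answers are reduced to 0/1, or if the direction is reversed in a one-sided test. Nor does it if a 0-25 score is pooled with a 0-100 score. In a plain average of the two dimensions (an illustration; the SAP gives no such rule), a full-range move in Satisfaction shifts the result by 100/2 = 50 points and one in Bother by 25/2 = 12.5.

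**6. Position in the hierarchy.** The order is 1, 2, 3, 4.1 to 4.6, 5.1 to 5.3, 6.1 to 6.3: 3 + 6 + 3 + 3 = 15 tests. Test 4.2 is fifth, so 15 - 5 = 10 follow it (4.3 to 6.3).

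**7. Symptom-Bother item 1.** Items 2-20 run from 0 (symptom absent or not applicable) to 4, and higher means more bother.
- If 0 on item 1 means *none of the time*, item 1 agrees with them and the effect is zero.
- If 0 means *all of the time*, item 1 runs the other way. A uniform change of k per item is scored 25 x (19k - k)/20 = 22.5k instead of 25k, a 10% shrinkage. The highest score becomes 25 x (19 x 4)/20 = 95 instead of 100, a 5-point shift.

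**The case against.** **The fault may lie in the copy, not in the SAP.** In the text as read from PDF, the scoring-procedure row of Table 4 repeats sentences and breaks off, and the Emotional Impact rule is absent. The singular *this item* after a plural subject, the lack of any scale for item 7, and the similar not-scored rule for filter item 22 all suggest that two lines were lost or merged. This stands as a caution: check the original page first. The two conflicting sentences are each complete as read.

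**A score missing for everyone would be noticed.** Probably so, since baseline IDEEL scores are tabulated and a blind data review precedes lock. But SAP 7.10 does not say that IDEEL scores are examined at that review, and the baseline table (14.1.8.1) belongs to the final analysis, after unblinding.

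**The link to test 4.2 is incomplete.** This stands. The module has two dimensions and two MMRM output tables (14.2.4.4.2.1 and 14.2.4.4.2.2), and nothing says how they give one p-value for 4.2. The test is also reached only if both co-primary endpoints and four earlier tests succeed.

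**Stronger readings a reader might infer, which the documents do not support:**
- *That the 0-25 range by itself makes test 4.2 fail.* It does not alter that dimension's p-value.
- *That the Bother score is reversed.* This depends on item wording that is not given.
- *That the items are meant to be 0-4 and the Yes/No rule belongs to item 7.* This is plausible by elimination, but 0/1 items times 100 also fit the stated range.
- *That Symptom Bother will be understated by 10%.* This takes the adverse repair of a duplicated label. The other repair agrees with items 2-20 and Table 5 and has no effect.

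**Conclusion.** As read, the scoring rule for Treatment-Related Bother is contradictory. It yields no score for any patient, or a 0-25 score where 0-100 is stated. That conclusion needs only the table's own rules, provided the original page reads the same way.

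The consequence for tests 4.2 and 4.5 is a possibility, not a demonstrated loss. It requires one of four things: a missing score, graded answers collapsed to 0/1, a reversed direction, or combination with Satisfaction on unequal scales. It also depends on a rule for combining the two dimensions that the SAP does not give. If it did occur at 4.2, ten later tests could no longer be claimed. The Symptom-Bother anchor, relevant to tests 4.3 and 4.6, has an effect between zero and a 10% shrinkage of a uniform change. The co-primary endpoints are untouched. The correction should be made because it is cheap now and harder to defend after unblinding.

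**What to change.** Check the original page of Table 4. If the text stands, then before database lock and unblinding:

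1. Reconcile the item-scaling row with the IDEEL manual to which SAP 7.8 refers.
2. Remove the exclusion from items 6 and 8-10. State their response scale, direction and multiplier, so that the score spans 0-100 and higher means less bother, as in Table 5.
3. Attach the Yes/No, not-scored rule to whichever item the manual names.
4. Correct the anchors of Symptom-Bother item 1 so that it runs in the same direction as items 2-20.
5. State how the two treatment dimensions produce the single p-value for tests 4.2 and 4.5.

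The cost is SAP wording and a programming check against the manual. No new data are needed.

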7.2.4 Full Analysis set (FAS)

The FAS population will consist of all randomized patients who received at least one dose of the investigational product. FAS population will be analyzed according to intention-to-treat (ITT) principle, i.e. by treatment allocation regardless happening of intercurrent events (treatment policy strategy). The FAS population will be used for the primary analysis of the study and to present results on efficacy data.

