#### 7.8 Handling of missing and incomplete data

All reasonable efforts will be made to reduce the rate of missing data. Investigators will be trained about the importance of patient retention and full data capture. Also, any reasonable attempts should be made by the investigators to emphasize continued subject's participation for the full duration of the trial.

Patients who discontinue the treatment will not be withdrawn from the study by default but will be asked to complete safety and efficacy observations as per the protocol, unless otherwise they withdraw their consent. Patients who discontinue study treatment and decide to remain in the study

by following the schedule of assessments and continuing to adhere to protocol requirements are defined as "retrieved drop-out" patients.

For the primary and key secondary analyses, missing data will be handled by means of Multiple Imputation using retrieve dropouts (MI-RD), as detailed in sections 10.1.2 and 10.2.2.

In addition, to further minimize missing data, if a patient cannot refer to the site for a planned followup visit, the investigator will try to obtain any relevant information from the patients, including documents/laboratory results available from local medical care.

The number of subjects with missing data will be presented under the "Missing" category. Missing values will not be included in the denominator count when computing percentages. When continuous data will be summarized, only the non-missing values will be evaluated for computing summary statistics.

For the analyses of parameters for which an independent blinded reading center may be involved per protocol, the following rules will be used:

- 1. If assessment from blinded reading center is available, such value will be used for the analysis.
- 2. If assessment form blinded reading center is not available, the corresponding evaluation (if any) from the site investigator will be used.
- 3. If both assessments (blinded reading center and site investigator) are not available, a statistical imputation method will be applied as described in this SAP.

Rules for handling missing data of IDEEL questionnaire are reported in section 12.3, according to the dedicated manual.

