# 10.2.2.1 Schirmer I test >10mm/5min at week 8

The proportion of patients reaching a value of Schirmer I test (without anesthesia) >10mm/5min at week 8 will be analyzed as described in section 10.1.2.1 for the primary efficacy endpoints.

# 10.2.2.2 Change from baseline in SANDE score for severity at week 12

The change from baseline in SANDE score for severity at week 12 will be analyzed as described in section 10.1.2.2 for the primary efficacy endpoints.

# 10.2.2.3 Change from baseline in SANDE scores for frequency at week 12

The change from baseline in SANDE score for frequency at week 12 will be analyzed as described in section 10.1.2.2 for the primary efficacy endpoints.

# 10.2.2.4 Change from baseline in IDEEL modules (Quality of Life, Dry eye Treatment satisfaction & Bother, and Dry eye Symptom bother) at week 12 and at week 4

Rules for derivation of IDEEL scores are reported in section 12.3. The change from baseline of each IDEEL module will be analyzed by means of an MMRM adjusting by pre-defined factors (gender, age class, IDEEL module baseline value, treatment, visit, and treatment by visit interaction; subject will be considered as a random effect). The covariance matrix used will be "unstructured". Comparisons versus vehicle TID will be provided using least square means at each visit and overall and a one-sided test will be used to test for differences between treatment groups.

For the imputation of missing data, a regression model will be created by including the baseline value, gender, age class, and intermediate scores up to week 12. Two hundred data sets will be generated, and the random seed number will be 225670. MI will be implemented in the following steps:

- 1. Partial imputation assuming MAR will be carried out to impute intermittent (non-monotone) missing data of IDEEL module score based on a multivariate joint Gaussian imputation model using the MCMC method. A separate imputation model will be used for each treatment arm. In case of non-convergence or non-estimability issues, a single imputation model will be considered (with treatment arm added as explanatory variable to the model). A total of 200 datasets will be created. These datasets will be utilized in Step #2.

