- 2. The remaining monotone missing data will be imputed using a MI regression including the same explanatory variables of the previous step. According to MI-RD approach, only non-missing values from retrieve dropouts will be used to inform the regression model.
- 3. Each of the 200 imputed datasets will be analyzed using observed and imputed data. Rubin's rule will be used for combining results to draw inference.

If there are not enough retrieved dropouts for convergence of MI-RD regression model, a Copy Reference approach will be adopted to consider a MNAR mechanism for missing data. The final decision on the use of the MI-RD vs Copy-Reference for this endpoint will be done at the time of the analysis and reported in the CSR.

Whether for MI-RD or Copy-Reference approach, the adjusted estimated treatment differences in means for IDEEL module scores between cenegermin and vehicle at each available timepoint will be displayed together with the corresponding two-side 95% confidence intervals and p-value.

# 10.2.2.5 Change from baseline in Cornea and conjunctiva vital staining with fluorescein NEI scale at week 4, week 8 and at week 12

Rules for derivation of NEI scores are reported in section 12.4. The change from baseline in Cornea and conjunctiva vital staining with fluorescein NEI scale will be analyzed by means of an MMRM adjusting by pre-defined factors (gender, age class, NEI scale baseline value, treatment, visit, and treatment by visit interaction; subject will be considered as a random effect). The covariance matrix used will be "unstructured". Comparisons versus vehicle TID will be provided using least square means at each visit and overall and a one-sided test will be used to test for differences between treatment groups.

For the imputation of missing data, a regression model will be created by including the baseline value, gender, age class, and intermediate scores up to week 12. Two hundred data sets will be generated, and the random seed number will be 569888. MI will be implemented in the following steps:

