| Table 14.2.4.4.1.3 Change from baseline in the IDEEL Quality of Life module (Work) up to week 12 - MMRM - Multiple imputation. Full analysis     |     | ×              |
| set  |     | ^              |
| Table 14.2.4.4.2.1 Change from baseline in the IDEEL Dry eye Treatment satisfaction & Bother module (Treatment – In General) up to week 12       |     | ×              |
| - MMRM - Multiple imputation. Full analysis set  |     | ^              |
| Table 14.2.4.4.2.2 Change from baseline in the IDEEL Dry eye Treatment satisfaction & Bother module (Treatment – Eye drops) up to week 12 -      |     | x              |
| MMRM - Multiple imputation. Full analysis set  |     | ^              |
| Table 14.2.4.4.3 Change from baseline in the IDEEL Dry eye Symptom bother module up to week 12 - MMRM - Multiple imputation. Full                |     | x              |
| analysis set   |     | ~              |
| Table 14.2.4.5 Change from baseline in the Cornea and conjunctiva vital staining with fluorescein NEI scale up to week 12 - MMRM - Multiple      |     | x              |
| imputation. Full analysis set  |     |                |
| Table 14.2.4.6 Change from baseline in the TFBUT up to week 12 - MMRM - Multiple imputation. Full analysis set                                   |     | x              |

| Number - Title - Population   | KFR | Final analysis |
|---|-----|----------------|
| Table 14.2.5.1 Absolute values and change from baseline in Schirmer I test at each timepoint. Full analysis set   | х   | x              |
| Table 14.2.5.2.1 Absolute values and change from baseline in SANDE global scores at each timepoint. Full analysis set   | х   | x              |
| Table 14.2.5.2.2 Absolute values and change from baseline in SANDE severity scores at each timepoint. Full analysis set   | х   | x              |
| Table 14.2.5.2.3 Absolute values and change from baseline in SANDE frequency scores at each timepoint. Full analysis set  | х   | x              |
| Table 14.2.5.3 Number of patients experienced a worsening in symptom scores (SANDE global score) and/or NEI score ≥ 50% assessed at week 4. Full analysis set   |     | x              |
| Table 14.2.5.4.1 Absolute values and change from baseline in IDEEL Quality of Life module at each timepoint. Full analysis set  | х   | x              |

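### The IDEEL Work score exists only for patients in work, but the SAP analyses it in the full analysis set with multiple imputation and does not separate not-applicable from missing

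*SAP*

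**What the plan says.** SAP 12.3, Table 4, makes the Impact on Work score depend on item 22, which asks whether the patient currently works. For a patient who answers No, "then items 23-27 are missing, and the Impact on Work score is missing".

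The table list in SAP 15.1 includes, as Table 14.2.4.4.1.3, "Change from baseline in the IDEEL Quality of Life module (Work) up to week 12 - MMRM - Multiple imputation", and assigns it to the full analysis set. SAP 7.2.4 defines that set without reference to employment: "The FAS population will consist of all randomized patients who received at least one dose of the investigational product".

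The missing-data rule in SAP 7.8 is general: "For the primary and key secondary analyses, missing data will be handled by means of Multiple Imputation using retrieve dropouts (MI-RD"). SAP 10.2.2.4 applies it to IDEEL in two steps. Step 1 fills intermittent gaps by MCMC. Step 2 fills all monotone gaps that remain by regression, where "only non-missing values from retrieve dropouts will be used to inform the regression model". The predictors are described thus: "For the imputation of missing data, a regression model will be created by including the baseline value, gender, age class, and intermediate scores", the last of these running to the week 12 visit. Item 22 is not among them. If MI-RD does not converge, Copy Reference is used. SAP 7.9 confirms that the IDEEL MMRM runs after this imputation.

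SAP 7.8 also refers the reader to 12.3 for IDEEL missing-data rules. Section 12.3 gives the rule that half the items must be completed and sets scores to missing. It does not say which of those missing scores are later exempt from imputation.

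**The concern.** A Work score for someone without work is not a value that was lost. It never existed, and no assumption about a missingness mechanism can recover it. The scoring rule nevertheless gives it the same missing code as a skipped questionnaire, and the imputation rule then acts on that code.

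If non-workers are imputed, the Work comparison covers a population for which the outcome has no meaning, and its imputed part is drawn from a handful of retrieved drop-outs or from vehicle patients. If the program drops them instead, the analysed set differs from the one printed in the table title, and its size depends on a programming choice. In both cases a reader of the Work table cannot tell whom the estimate describes.

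Table 4 does score not-applicable answers explicitly for some individual items in the Daily Life and Symptom-Bother modules. The distinction is thus recognised at item level but not carried through to the Work score.

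**Working it through.** **Plan figures used as denominators.** The SAP gives no figure for the Work score or for employment. Its sample-size figures (section 5) are used here only for patient numbers, and they reproduce:
- Enrolment: 72 / 0.90 = 80.
- Schirmer I, 36 per arm, 33% against 75%, one-sided 0.025, pooled variance: Φ[(0.42 − 1.96·√(2·0.54·0.46/36)) / √((0.33·0.67 + 0.75·0.25)/36)] = 96.3% (stated 96.3%).
- SANDE, difference 10, SD 12: Φ[10/(12·√(2/36)) − 1.96] = 94.2%, or 93.7% with the noncentral t (stated 94.1%).

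**Tracing the rules by type of patient.**
- Never in work: no Work value at baseline or at any visit. Nothing observed follows a gap, so the pattern is monotone and falls under step 2.
- Not in work at baseline, working later: a non-monotone pattern, so step 1 would impute the baseline.
- In work, then stops for good: monotone from that visit, so step 2.
- Stops and restarts: an intermittent gap, so step 1.

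Every type therefore meets an imputation step, and no sentence takes any of them out. SAS code is given only for the two co-primary endpoints (SAP 15.4). Its step-2 calls list the baseline value among the variables of the imputation procedure. If the IDEEL program follows that template, a missing baseline is not a bar to entry.

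**How many patients.** Assumption: 30% to 60% not working.
- 0.30 × 80 = 24 and 0.60 × 80 = 48 patients with wholly imputed Work scores.

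**Which imputation method would apply.** Suppose all 10% × 80 = 8 non-evaluable patients were retrieved drop-outs. With 30% to 70% of them working, 8 × 0.30 = 2.4 to 8 × 0.70 = 5.6 would have real Work scores. The regression would have about eight coefficients: intercept, arm, age class, gender, baseline, and weeks 2, 4 and 8. MI-RD would probably not be estimable, so Copy Reference would probably be used.

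**Dilution under Copy Reference with imputed baselines.** Let w be the share working and δ the effect in workers. Imputed non-workers in both arms follow the vehicle model, so their expected difference is zero:

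E(estimate) = w·δ + (1 − w)·0 = w·δ

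With 30% to 60% not working, the estimate is 0.70δ to 0.40δ.

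**Illustrative simulation.** 36 per arm, effect 10/12 = 0.83 SD (borrowed from SANDE, an assumption for Work), baseline correlation 0.5, 600 runs, 30 imputations, Rubin's rules. Copy Reference with imputed baselines is built in.

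| Share working | Workers of 72 | Workers only: estimate, power | Full set, Copy Reference: estimate, power |
|---|---|---|---|
| 30% | about 22 | 0.84, 55% | 0.26, 2% |
| 50% | 36 | 0.84, 80% | 0.42, 24% |
| 70% | about 50 | 0.84, 91% | 0.58, 71% |

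With no true effect, the full-set analysis rejected in at most 0.2% of runs, against the nominal 2.5%. The simulation shows the size of the dilution if that route is taken. It does not show that the route will be taken.

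**The case against.** The strongest reply is that the SAP never says it imputes for non-workers. The outcome is a change from baseline with the baseline as a covariate, and a patient who never works has no baseline. Such patients might fall out of the MMRM, which comes close to the restriction proposed here. The specific IDEEL rule, via 12.3 and the instrument's manual, leaves the score missing, and a specific rule might be read as overriding the general one.

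Part of this stands. Imputation of non-workers follows from the absence of a restriction, not from an explicit statement, and no IDEEL code settles it. But silent exclusion contradicts a table that names the full analysis set and multiple imputation. The reference to 12.3 only determines when a score is missing; what happens next is governed by 10.2.2.4.

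A reader might also infer four stronger things that the documents do not support:
- That Work is a gated confirmatory result. Steps 4.1 and 4.4 in SAP 10.2.2 name one p-value each for the Quality of Life module. Section 12.3 lists Work as a section of that module and 15.1 gives it its own table, but no text says how, or whether, Work enters the module p-value.
- That the effect shrinks by a fixed 30% to 60%. This needs the assumed non-working share, imputed baselines and Copy Reference together. MI-RD, the planned method, includes the allocated arm in the model described for the co-primaries and has no fixed shrinkage; its weakness is extrapolation from very few patients.
- That the flaw could produce a false claim of benefit. Under Copy Reference the null simulation points the other way.
- That Treatment Satisfaction has the same problem to the same degree. That score is missing for patients who never treat their dry eyes, but inclusion criterion 10 requires ongoing topical cyclosporine or a drug of its class, so the case should be rare.

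**Conclusion.** The point holds in a limited form. A score defined only for working patients is assigned to an analysis set that ignores employment, under imputation rules that do not separate not-applicable from missing. Read literally, the rules impute Work scores for non-workers; on a different programming choice those patients vanish from a table that claims to include them.

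On the assumption that 30% to 60% do not work, 24 to 48 of 80 patients are affected. If Copy Reference and imputed baselines also apply, the Work estimate is diluted to about 70% to 40% of the effect in workers. The harm is lost power and an estimate that cannot be interpreted. The co-primary conclusions do not depend on it, and an effect on the gated sequence is not established. It should be corrected because the correction is cheap and the table is uninterpretable without it.

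**What to change.** Amend SAP 10.2.2.4 and the Work entry in 15.1 before unblinding:
1. Define the Work analysis set as full-analysis-set patients who answer Yes to item 22 at baseline, and name that set in the table title.
2. Within it, impute only Work scores that could have existed and were not obtained. Do not impute for patients not working at baseline, including those who start work later.
3. Prespecify how stopping work after baseline is handled. It may be a consequence of dry eye, so simply deleting those visits would condition on a post-randomisation event. Observed-value handling cannot help, because no score exists after work stops; the SAP should choose and justify a strategy, and tabulate by arm how many patients stopped and why.
4. State whether Work contributes to the Quality of Life module p-value in steps 4.1 and 4.4.

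The cost is a few sentences of SAP text and a flag from item 22, which the questionnaire already collects. The downside is a smaller Work analysis: at 30% to 60% not working, 56 to 32 of 80 patients (80 − 24 and 80 − 48), with correspondingly wider intervals.
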